6.11.2 Laboratory Test

Laboratory data will be summarized by presenting summary statistics of raw data and change from baseline values (means, medians, standard deviations, ranges). For quantitative laboratory parameters, both actual values and change from baseline values will be summarized at each visit.

Shift tables will be presented, in which, lab test results at baseline and post-baseline visit will be classified into below (\leq LLN), within (\geq LLN and \leq ULN), and above (\geq ULN) normal ranges. Subject incidences (n and %) will be presented for the shift from baseline to the post-baseline visits.

Note that the analysis window will be applied for the visits.

A complete laboratory data listing, including hematology, biochemistry, and urinalysis will be provided for all subjects.

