11.3 Blinding

The identity of test and control treatments will not be known to Investigators, Sponsor, research staff, subjects, or the study monitor. The following study procedures will be in place to ensure double-blind administration of study treatments:

- Access to the randomization codes will be strictly controlled by the IRT system.
- Throughout the double-blind study, the blind should remain unbroken except for an emergency when knowledge of the subject's study medication is necessary for further management or if required for regulatory reporting. The Medical Monitor approves any emergency blind break, if at all possible, prior to the unblinding.
- The lirentelimab SC and placebo SC administered by SC injection will be identical in appearance.
- Results from the analysis of blood samples for PK and ADA will not be provided to the Investigator and Sponsor until after final database lock of the double-blind study.
- Results from the analysis of blood samples for histamine/tryptase tests (collected in case of possible anaphylaxis) will not be provided to the Investigator and Sponsor until after final database lock of the double-blind study, unless required for immediate safety reasons.
- Results of the assessments noted below will not be provided to the Investigator and Sponsor until after final database lock of the double-blind study to avoid bias. The results will be reviewed on an ongoing basis by the Safety Monitor and escalated as appropriate.
 - Differential cell counts including neutrophils, eosinophils, basophils, monocytes, and lymphocytes.

Other than under the conditions described above, the study blind will be revealed on completion of the study as noted in Section 17.4.

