12.1.10 Complete Blood Count with Differential

Blood for CBC with differential, including absolute blood eosinophil count, will be obtained at screening, just prior to each SC injection, and 1 hour (±15 minutes) after the end of each SC injection, as well as on all follow-up days 85, 127, and 155 (±5) or 14, 56, and 84 (±5) days after last dose, if ET. The blood sample will be processed and shipped in accordance with the Laboratory Manual and lab kit instructions. A central laboratory will analyze the blood sample and provide results for CBC with differential including hemoglobin, hematocrit, platelet count,

red blood cell count, white blood cell count, and absolute differential count (neutrophils, lymphocytes, monocytes, eosinophils, and basophils).

During the double-blind period, all differential blood counts from Day 1 (post-dose) through the end of the subject's participation will be blinded to the Sponsor and the site. An unscheduled CBC may be collected at the request of the Safety Monitor. The blood differential test results (neutrophils, eosinophils, basophils, monocytes, and lymphocytes) will be blinded from the Investigator and Sponsor from post-dose Day 1 through Day 155 or ET and until database lock has occurred. If a subject continues to the OLE period of the study, all differential blood counts will be blinded for the first (OLE Day 1) predose assessments and will be unblinded after the subject has received the first dose of the study drug.

As described in the Investigator's Brochure, changes in certain lab results are a part of the expected effects of lirentelimab and could potentially introduce bias in blinded members of the study. The Safety Monitor will have real-time access to these laboratory results and will review and escalate any concerns/issues to the Medical Monitor and/or the site as appropriate. An unscheduled CBC with differential may be collected if requested by the Safety Monitor. All panic alerts for blinded values will be sent to the Safety Monitor and evaluated in real time.

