12.3 Clinical Laboratory Measurements

Blood and urine samples for clinical safety laboratory tests will be collected at the time points described below. Investigators may have additional laboratory tests performed for the purpose of planning treatment administration or following AE or abnormal laboratory values.

The site will process and ship blood and urine samples per central laboratory instructions. A central laboratory or designee will analyze blood and urine samples and provide results for the following clinical safety laboratory tests.

Clinical laboratory testing may be performed locally, if necessary, with prior approval from Allakos. The site will strive to use the central laboratory whenever possible.

For any laboratory test value outside the reference range, the Investigator will determine clinical significance: Not Clinically Significant (NCS) or Clinically Significant (CS). An abnormal laboratory value should be deemed CS if any of the following conditions are met:

- The abnormality suggests a disease and/or organ toxicity that is new or has worsened from baseline.
- The abnormality is of a degree that requires additional active management, e.g., change of study drug dose, discontinuation of the study drug, close observation, more frequent follow-up assessments, or further diagnostic investigation.

Therefore, a clinically significant lab value is one that indicates a new disease process, an exacerbation or worsening of an existing condition, or requires further action to be taken. For any laboratory test value outside the reference range that the Investigator considers clinically significant, the Investigator will:

- Repeat the test to verify the out-of-range value.
- Follow the out-of-range value to a satisfactory clinical resolution.

- Record as an AE any laboratory test value after start of study drug that:
 - The Investigator considers clinically significant.
 - Requires a subject to be discontinued from the study.
 - Requires a subject to receive treatment.

Blood will be obtained for CBC with differential as described in Section 12.1.10.

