6.11.3 Vital Signs, Height and Weight, and Other Safety Measures

Vital signs will be summarized by presenting summary statistics of raw data and change from baseline values (means, medians, standard deviations, ranges) for each visit (per analysis window) and time point. A data listing will include vital signs from all visits.

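### No graded or worst-post-baseline laboratory comparison of neutrophils and lymphocytes is planned, although sites are blinded to these counts and AE capture depends on escalation with no stated threshold

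*SAP*

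**What the plan says.** **Who sees the counts.** Protocol Section 12.1.10 states that "differential blood counts from Day 1 (post-dose) through the end of the subject's participation will be blinded to the Sponsor and the site". Section 11.3 names what is withheld until after final lock: "Differential cell counts including neutrophils, eosinophils, basophils, monocytes, and lymphocytes". Total white count, hemoglobin and platelets are not on that list. The Safety Monitor sees the results in real time and "will review and escalate any concerns/issues to the Medical Monitor and/or the site as appropriate". Section 12.1.10 adds: "All panic alerts for blinded values will be sent to the Safety Monitor and evaluated in real time". The Safety Monitor may also ask for an unscheduled CBC.

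**How a count becomes an AE.** Protocol Section 12.3 tells the Investigator: "Record as an AE any laboratory test value after start of study drug that" is judged clinically significant, requires discontinuation, or requires treatment.

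**What the SAP tabulates.** Section 6.11.2 plans actual values and change from baseline at each visit (means, medians, standard deviations, ranges), a complete listing, and a shift table: "Shift tables will be presented, in which, lab test results at baseline and post-baseline visit will be classified into below", within or above the normal range. In Appendix 2 these are Table 14.3.2.1 (change from baseline) and Table 14.3.2.3 (shift). Section 5.1 presents all summaries by arm. The only graded safety output is TEAE by maximum severity (Section 6.11.1), which covers reported AEs.

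**Grading scale.** The protocol uses CTCAE v5 for AE severity, and its Appendix 6 prints neutrophil and lymphocyte cut-offs. The SAP does not apply them to laboratory values.

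**The concern.** For most laboratory tests, a coarse shift table is backed up by the AE tables: the site sees a markedly abnormal value, judges it, and reports a graded event. For differential counts that backing is weaker. The main test in Protocol Section 12.3 is whether "the Investigator considers clinically significant" applies to the value, and a site cannot judge a value it has not been shown. It cannot make good the omission later either, because results are released only after final lock, when the database is write-protected (Protocol Section 17.4, SAP Section 5.6). What reaches the AE page depends on what the Safety Monitor chooses to pass on.

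The laboratory tables therefore have to show by themselves how many subjects in each arm had a deep fall in neutrophils or lymphocytes, and as planned they do not. Laboratory values and TEAEs are a listed secondary endpoint (SAP Section 2.2). Protocol Section 12.1.10 acknowledges that some laboratory changes are expected effects of the drug, and opportunistic infection is an AE of special interest (Section 14.3). An imbalance in graded cytopenia is something readers of the study report would want to see or rule out.

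**Working it through.** The plan states no figure on this point, so there is none to reproduce. The check traces the two routes by which a low count could appear in a comparison between arms, then illustrates the loss under labelled assumptions.

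**1. AE route.** Site judgement is closed for differentials (Sections 11.3 and 12.1.10). Escalation is open, but no grade threshold and no rule for recording an escalated value as an AE is given. The share of low counts that would be recorded is unknown.

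**2. Laboratory route.** Protocol Appendix 6 set against the SAP classes (counts per mm3; LLN = lower limit of normal):

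| CTCAE v5 grade | Lymphocytes | Neutrophils | SAP class |
|---|---|---|---|
| 1 | below LLN to 800 | below LLN to 1500 | below |
| 2 | below 800 to 500 | below 1500 to 1000 | below |
| 3 | below 500 to 200 | below 1000 to 500 | below |
| 4 | below 200 | below 500 | below |

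**3. Data available.** Samples after the first dose for a subject outside the OLE: Day 1 post-dose (1), predose and 1 hour post-dose on Days 15, 29, 43, 57 and 71 (5 × 2 = 10), and Days 85, 127 and 155 (3). Total 1 + 10 + 3 = 14. For a subject entering the OLE at Day 85 it is 1 + 10 + 1 = 12.

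**4. Loss within a visit (assumed counts, 65 per arm).** Suppose 13 subjects in each arm are below normal at a visit. The classification shows 13 v 13. If Grade 3 or worse splits 6 v 0, a graded table shows 6/65 = 9.2% v 0%. At 4 v 0 it is 6.2% (Fisher p = 0.12), at 6 v 0 p = 0.028, and at 10 v 0 it is 15.4% (p = 0.0013). Starting from 20 v 20 below normal changes none of this. Safety is descriptive in this trial, so the p-values only gauge size.

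**5. Loss across visits.** If six active subjects each reach Grade 3 once, at six different visits, any single visit has at most 1/65 = 1.5% at that grade, while worst post-baseline grade gives 6/65 = 9.2%. A by-visit range shows the lowest value in the arm, not how many subjects were that low or whether they were different subjects.

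**6. Values that can drop out.** When several unscheduled or early-termination values belong to one visit, SAP Section 5.2 keeps the one closest to the target day. An abnormal CBC requested by the Safety Monitor can be lost from the by-visit tables this way, though it stays in the listing.

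**7. Two samples per dosing visit.** Section 6.11.2 summarises by visit and does not say whether the predose or the 1-hour sample is used. Section 6.11.3 does specify this for vital signs: "for each visit (per analysis window) and time point". Section 6.11.2 also refers to an analysis window, which Section 5.2 says will not be defined for by-visit assessments.

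**8. What the AE tables might hold.** Expected recorded Grade 3+ cases in the active arm = 65 × true rate × share escalated and recorded. Both inputs are assumptions; results are to one decimal.

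| True rate | True cases | 10% recorded | 25% | 50% | 100% |
|---|---|---|---|---|---|
| 5% | 3.3 | 0.3 | 0.8 | 1.6 | 3.3 |
| 10% | 6.5 | 0.7 | 1.6 | 3.3 | 6.5 |
| 15% | 9.8 | 1.0 | 2.4 | 4.9 | 9.8 |

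The documents do not say which column applies.

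**The case against.** The strongest reply is that the SAP delivers what the protocol promised. Protocol Section 16.7.3 asks for descriptive statistics by visit and shift tables against normal ranges, and nothing there or in Appendix 6 commits to grading laboratory data by program. CTCAE is adopted for AE severity. The study is a proof-of-concept Phase 2 with no formal inference on safety. All of this stands: there is no contradiction and no broken commitment, and the change is an improvement.

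Several stronger readings are tempting, and the documents do not support them.

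- *The shift table is the only hematology comparison, or the only use made of the CBCs.* By-visit values and changes from baseline with ranges are planned by arm, and so are full listings. A single very low count would show as a minimum. What is missing is a count of subjects by grade.
- *Cytopenia cannot become a TEAE, so those tables will be empty.* Escalation, panic alerts and unscheduled CBCs all exist, and marked falls are the likeliest to use them. Total white count is not withheld. Opportunistic and parasitic infections are captured whether or not counts are blinded. Capture is uncertain; it is not shown to be nil.
- *AE rates in the OLE will look higher because sites then see the counts.* Ascertainment does differ once counts are unblinded after the first OLE dose, but this SAP lists no OLE tables and plans no such comparison.
- *The protocol expects counts not to recover.* Its extended follow-up in Section 20.9.1 is conditional. The described target is eosinophils and mast cells, and neutrophils are not named as a target.

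**Conclusion.** The point holds in a limited form. AE capture of neutropenia and lymphopenia in the double-blind period depends on escalation with no stated threshold. The only categorical laboratory comparison merges CTCAE grades 1 to 4 and works visit by visit, and no laboratory-derived graded or worst-post-baseline comparison between arms is planned.

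The consequence cannot be sized from the documents, which give neither cytopenia rates nor an escalation rate. Under the assumed counts above, a 6 v 0 difference in Grade 3+ subjects is compatible with an identical below-normal count in the two arms. That shows what the categorical table can miss; it does not predict that such a difference will occur. The by-visit means, ranges and listings would give partial signals. This is a low-cost gap worth closing before unblinding, and it does not affect the efficacy analysis.

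**What to change.** Amend SAP Section 6.11.2 and the table list in Appendix 2:

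1. After unblinding, derive CTCAE v5 grades from all central-laboratory post-baseline values, scheduled and unscheduled, for at least neutrophils and lymphocytes.
2. Tabulate by arm the worst post-baseline grade and the shift from baseline grade to worst grade. State that the closest-to-target-day rule of Section 5.2 does not apply to these tables.
3. Summarise predose and 1-hour post-dose CBCs separately in the by-visit tables.
4. Footnote the TEAE tables to say that post-dose differential counts were withheld from sites in the double-blind period.

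Blinding, the Safety Monitor's role and clinical management stay as they are. The cost is SAP wording, one derived variable and about two tables, with no new data. The downside for the sponsor is that laboratory toxicity may look less favourable than in the planned tables.

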6.11.3 Vital Signs, Height and Weight, and Other Safety Measures

Vital signs will be summarized by presenting summary statistics of raw data and change from baseline values (means, medians, standard deviations, ranges) for each visit (per analysis window) and time point. A data listing will include vital signs from all visits.

6.11.4 Electrocardiogram

Incidence of the Investigator's overall assessment (normal, abnormal – not clinically significant, and abnormal – clinically significant) will be summarized.

6.11.5 Physical Examination

New or worsening symptoms in the symptom-directed physical exams will be included in the by -subject data listing.

6.11.6 Analysis of Anti-Drug Antibodies

A data listing of anti-drug-antibodies (ADA) results will be provided for all subjects. Number (%) of subjects who are confirmed ADA-positive at any time after receiving study drug and number (%) of

subjects who are confirmed ADA-positive at the end of study will be cross-tabulated by their ADA status and titers at predose.

7. Validation

The Clinical Operations and Data Management at Allakos will work with the EDC/Data Management (DM) vendor to ensure that the data collected for the study is of the highest quality possible. The study monitor will be responsible for reviewing and verifying the accuracy of the data recorded on the eCRF directly from source documents at the investigative site. The DM vendor will be responsible for performing edit checks and reviewing all data entered into the electronic database to identify discrepant and/or inconsistent values and to send queries to the clinical sites. The Investigator will be responsible for answering queries about discrepant data and providing electronic signatures to confirm data integrity.

The programming of tables, listings, and figures (TLF) based on the clinical data is outsourced. Allakos seeks to ensure the quality of the reports provided by the CRO in the form of TLF passing a rigorous validation process as follows:

- Derived datasets will be independently reprogrammed by a second programmer. The separate datasets produced by the 2 programmers must match 100%.
- Tables will be independently reprogrammed by a second programmer, and the results from both programs must match.
- Figures will be checked for consistency against corresponding tables and listings or independently reprogrammed if there are no corresponding tables or listings.
- Listings will be checked for consistency against corresponding tables, figures, and derived datasets.

All post-hoc analysis, if accepted for inclusion in the study report, will follow the same quality process as stated above. The entire set of TLF will be checked for completeness and consistency prior to delivery to Allakos.

8. References

Food and Drug Administration. E9 (R1) Statistical Principles for clinical trials: addendum: estimands and sensitivity analysis in clinical trials. Guidance for industry, ICH, May 2021.

International Council for Harmonisation (ICH). Guideline for industry E3, structure and content of clinical study reports, July 1996.

9. Appendices

9.1 Appendix 1: Intercurrent Events and Listing of Prohibited Medication/Treatments and Potential Rescue Medications for CSU

9.2 Appendix 2: List of Tables, Figures, and Listings

9.1 Appendix 1: Intercurrent Events and Listing of Prohibited Medication/Treatments and Potential Rescue Medications for CSU

Prohibited medications are defined as therapies that should not be taken during the course of the study either because of a potential impact on the assessment of efficacy and/or subject safety. Rescue medications/treatments are defined as any therapy or treatment taken during the course of the study for the specific purpose of alleviating CSU symptoms that may have an impact on the assessment of efficacy and includes: systemic medications such as systemic corticosteroids, increased daily dose or addition of a new H1-AHs, immunosuppressants, immunomodulatory medications, and biologics. Detailed definitions of ICE and data handling strategy for ICE are described in section 4.2.5.

The following provides the details of the prohibited medications/therapies for this study:

- The use or initiation of any new H1-AH or increase in the total daily dose, as compared to baseline, of an H1-AH for the purpose of treating CSU at any point in the study will be considered rescue therapy H1-AH: ATC code is R06A
- 2) The use or initiation of topical corticosteroids for the purpose of treating skin conditions other than CSU at any point in the study will be not be considered rescue therapy but should be avoided if possible. If unavoidable, lower potency topical steroids over the least surface area possible and for the shortest duration should be utilized: ATC code is D07A High Potency TCS: ATC codes D07AC or D07AD Low or moderate potency TCS: ATC code D07, excluding D07AC or D07AD
- Prohibited systemic medications (including systemic corticosteroids, H2-AH, immunosuppressants, immunomodulators, hydroxychloroquine, oral doxepin, IV immunoglobulins, and biologics)

Systemic corticosteroids: ATC code is H02 H2-AHs: ATC code is A02BA Immunosuppressants or immunomodulators: ATC code is L04 Mycophenolate: ATC code is L04AA06 Methotrexate: ATC code is L04AX Interferons: gamma: ATC code is L03AB where Preferred Terms include interferon gamma, interferonalfa-2b Leukotriene inhibitors: ATC code is R03DC where Preferred Term includes Ibudilast, Montelukast, Pranlukast, and Zafirlukast Oral calcineurin inhibitors: ATC code is L04AD where Preferred Term includes Ciclosporin, Cyclosporin, Tacforius, Tacrolimus, Voclosporin Hydroxychloroquine: ATC code is P01BA02 Oral doxepin: ATC code is N06AA12 IV immunoglobulins: ATC code is J06B Janus Kinase inhibitors (JAKi): ATC code is L01EJ where Preferred Term includes Delgocitinib, Fedratinib, Pacritinib, Ruxolitinib and ATC code is D11AH with Preferred Term Abrocitinib

TNF inhibitors: ATC code is L04AB where Preferred Term includes Adalimumab, Afelimomab, Certolizumab, Etanercept, Golimumab, Infliximab, Opinercept, Ozoralizumab

Biologics:

Agents For CSU, Excluding Corticosteroids: ATC code is D11A where preferred terms include Dupilumab, Tralokinumab

CD20 inhibitors: ATC code is L01F where preferred terms include Obinutuzumab, Ofatumumab

Selective Immunosuppressants: ATC code is L04AA where preferred terms include Abatacept, Abetimus, Alemtuzumab, Anifrolumab, Apremilast, Baricitinib, Begelomab, Belatacept, Belimumab, Belumosudil, Deucravacitinib, Eculizumab, Efalizumab, Emapalumab, Filgotinib, Fingolimod, Inebilizumab, Itacitinib, Natalizumab, Ocrelizumab, Ofatumumab, Ozanimod, Peficitinib, Pegcetacoplan, Ponesimod, Ravulizumab, Sutimlimab, Teprotumumab, Teriflunomide, Tofacitinib, Upadacitinib, Vedolizumab Interleukin Inhibitors: ATC code is L04AC where preferred terms include Anakinra, Basiliximab, Bimekizumab, Briakinumab, Brodalumab, Canakinumab, Daclizumab, Guselkumab, Ixekizumab, Netakimab, Olokizumab, Rilonacept, Risankizumab, Sarilumab, Satralizumab, Secukinumab, Siltuximab, Sirukumab, Spesolimab, Tildrakizumab, Tocilizumab, Ustekinumab

Unspecified Immunosuppressants: No ATC code with Preferred Term including Barzolvolimab, Fezakinumab, Fletikumab, Gevokizumab, Gusacitinib, Ladarixin, Lebrikizumab, Ligelizumab, Mirikizumab, Nemolizumab, Olamkicept, Tabalumab, Tregalizumab

Biologics for Airway Disease and other indications: ATC code R03D with Preferred Term including Benralizumab, Mepolizumab, Omalizumab, Reslizumab, Roflumilast, Tezepelumab and ATC code is R03DX with Preferred Term including Rituximab

Other potential treatments for CSU:

The use of plasmapheresis, ultraviolet A or B (UVA or UVB), psoralen + UVA (PUVA), other phototherapy is not permitted during the study. The use of a tanning bed will not be considered rescue therapy or an ICE.

